5.2.3 Safety Analysis Set

The safety analysis set (SafAS) is defined as those subjects who have received at least 1 dose of the study vaccine and have any safety data available.

All subjects will have their safety analyzed after each dose according to the vaccine they actually received at that dose. For ‘any dose’ safety analyses, all subjects will have their safety analyzed according to the vaccine received at the first dose.

Safety data recorded for a vaccine received out of protocol design will be excluded from the analysis (and listed separately).

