***Steps 5 through 10 for all subjects***

Visit 1 (1 [+4] days after Visit Day 0): Inclusion, Blood Sampling (BL), and Vaccination:

- 4) Review warnings and precautions to vaccinations.
- 5) Review contraindications to vaccination
- 6) Contact the IRT system for randomization / allocation of subject number / vaccine assignment
- 7) Administer the appropriate study vaccines per Operating Guidelines. Each vaccine should be administered in an assigned location and documented appropriatelyc.

---

a The results of CBC and biochemistry laboratory tests, performed for the subject in terms of routine practice, can be used, if the tests were done within 7 days before Visit 0. In this case, the blood sample volume collected at Visit 0 will be 4 mL.

b The results of urine laboratory tests, performed for the subject in terms of routine practice, can be used if the tests were done within 7 days before Visit 0. In this case, no urine sample will be collected at Visit 0.

c Failure to administer vaccines in the designated limb will not constitute a protocol deviation, but should be recorded as a comment in the CRF. If the initial vaccines are administered in the wrong limbs, this should be corrected for subsequent injections.

- **Groups 3 and 4:** Prevnar 13®: inject IM into the anterolateral area of the thigh (preferably the left thigh)a
- 8) Keep the subject under observation for 30 minutes and record any AE in the source document.
  - 9) Give the parent a diary card (DC1), a thermometer, and a ruler, and go over the instructions for their use.
  - 10) Remind the parent to expect a telephone call 8 days after Visit 1 and to bring back the diary card when they return for Visit 2 at a specified date and time.
  - 11) Remind the parent to notify the site in case of an SAE.
  - 12) Complete the relevant CRFs for this visit.

Telephone Call 1 (8 [+2] days after Visit 1)

**Note:** If Day 8 falls on a weekend or a holiday, the telephone call may be made on the following business day.

- 1) Record relevant information concerning the subject's health status on the telephone contact form. If an SAE has occurred that has not yet been reported, follow the instructions in [Section 10](#) for reporting it.
- 2) Remind the parent to do the following:
  - Complete the D0 to D07 pages of the diary card.
  - Complete the remaining pages of the diary card, and bring them to the next visit.

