#### 12.2.2 Safety Analysis Set

The safety analysis set (SafAS) is defined as those subjects who have received at least 1 dose of the study vaccinea and have any safety data available.

All subjects will have their safety analyzed after each dose according to the vaccine they actually received at that dose. For ‘any dose’ safety analyses, all subjects will have their safety analyzed according to the vaccine received at the first dose.

Safety data recorded for a vaccine received out of protocol design will be excluded from the analysis (and listed separately).

---

a for which safety data are scheduled to be collected

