- 7) To describe the antibody titers to the antigens (meningococcal serogroups A, C, Y, and W) present in MenACYW conjugate vaccine and Menveo[®] measured by rSBA before the first vaccination (Visit 1) and 30 days after the last vaccination in the second year of life, when administered concomitantly with routine pediatric vaccines in a subset of subjects (100 subjects in Group 1, and 50 subjects in Group 2) in Mexico
- 8) To describe the antibody titers to the antigens (meningococcal serogroups A, C, Y, and W) present in MenACYW conjugate vaccine measured by rSBA before the first vaccination (Visit 1) and 30 days after the last vaccination in the second year of life, when administered concomitantly with routine pediatric vaccines in a subset of subjects (100 subjects in Group 3) in the Russian Federation

Observational Objective(s)

Safety

- 1) To describe the safety profile of MenACYW conjugate vaccine and Menveo[®] when administered concomitantly with routine pediatric vaccines in healthy infants and toddlers in Mexico (Group 1 vs Group 2)
- 2) To describe the safety profile of MenACYW conjugate vaccine when administered concomitantly with routine pediatric vaccines in healthy infants and toddlers in the Russian Federation (Group 3)
- 3) To describe the safety profile of routine pediatric vaccines in healthy infants and toddlers in Mexico (Groups 1 and 2) and the Russian Federation (Groups 3 and 4)

3 Description of the Overall Trial Design and Plan

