3.1 Study Design

This is a Phase III, open-label, randomized, parallel-group, active-controlled, multi-center study to describe the immunogenicity and safety of a 3-dose immunization schedule of MenACYW conjugate vaccine or a 4-dose immunization schedule of a licensed quadrivalent meningococcal conjugate vaccine (Menveo[®] [Meningococcal {Groups A, C, Y and W-135} Oligosaccharide Diphtheria CRM₁₉₇ Conjugate Vaccine]) when administered concomitantly with routine pediatric vaccines (Prevnam 13[®], Hexacima[®], RotaTeq[®], and M-M-R[®]II) in healthy infants and toddlers aged 2 to 12 months in Mexico, and to describe the immunogenicity and safety of a 3-dose immunization schedule of MenACYW conjugate vaccine when administered concomitantly with routine pediatric vaccines (Prevnam 13[®], Pentaxim[®], ENGERIX-B[®], and MMR) in healthy infants and toddlers aged 2 to 12 months in the Russian Federation.

A total of 525 subjects will be enrolled. Approximately 300 healthy, meningococcal-vaccine naïve infants aged 2 months will be randomized in a 2:1 ratio in Mexico, and 225 healthy,

-
- Confidential/Proprietary Information
 - Page 9 of 67

meningococcal-vaccine naïve infants aged 2 months will be randomized in a 2:1 ratio in the Russian Federation into the following groups:

Mexico

- Group 1: MenACYW conjugate vaccine at 2, 6, and 12 months of age + routine pediatric vaccines at 2, 4, 6, and 12 months of age
- Group 2: Menveo[®] at 2, 4, 6, and 12 months of age + routine pediatric vaccines at 2, 4, 6, and 12 months of age

The Russian Federation

- Group 3: MenACYW conjugate vaccine at 3, 6, and 12 months of age + routine pediatric vaccines at 2, 3, 4.5, 6, and 12 months of age
- Group 4: Routine pediatric vaccines at 2, 3, 4.5, 6, and 12 months of age

All subjects in Groups 1 and 2 will receive either MenACYW conjugate vaccine or Menveo[®] concomitantly with the following routine pediatric vaccines in accordance with available official recommendations *in Mexico*:

- Prevnar 13[®] (pneumococcal 13-valent conjugate vaccine [PCV13]) at 2, 4, 6, and 12 months of age*
- Hexacima[®] (DTaP-IPV-HB-Hib) at 2, 4, 6, and 12 months of age
- RotaTeq[®] (pentavalent rotavirus vaccine [RV5]) 2, 4, and 6 months of age
- MMR (measles, mumps, rubella [MMR] vaccine) at 12 months of age

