Group 1	MenACYW [†] Pevnar 13 [®] Hexacima [®] RotaTeq [®] BL0001 (Pre-Vaccination)	Pevnar 13 [®] Hexacima [®] RotaTeq [®]	MenACYW [†] Pevnar 13 [®] Hexacima [®] RotaTeq [®]	BL0002	MenACYW [†] Pevnar 13 [®] Hexacima [®] M-M-R [®] II	BL0003
Group 2	Menveo [®] Pevnar 13 [®] Hexacima [®] RotaTeq [®] BL0001 (Pre-Vaccination)	Menveo [®] Pevnar 13 [®] Hexacima [®] RotaTeq [®]	Menveo [®] Pevnar 13 [®] Hexacima [®] RotaTeq [®]	BL0002	Menveo [®] Pevnar 13 [®] Hexacima [®] M-M-R [®] II	BL0003

*Per the current National Immunization Program (NIP) and Health Authority recommendations in Mexico, the varicella vaccine is administered at or after 12 months of age; it is not administered within the scope of the study. However, VARIVAX[®] vaccine will be provided by the Sponsor as a benefit vaccine as per standard practices and the current recommendations of the NIP in Mexico. The study personnel / Investigator will be responsible for administering this vaccine at V6 after the last blood sample (BL0003) of the study. No endpoints will be measured for this vaccine, even if it is administered at V6 of the study.

[†]MenACYW conjugate vaccine

Table 3.2: Vaccination, BL, and urinalysis schedule: the Russian Federation (Groups 3 and 4)

Visit (V)	V0	V01	V02	V03	V04	V05	V06	V07
Subject Age	2 months	2 months	3 months	4.5 months	6 months	7 months	12 months	13 months
Group 3	BL0001 (6 mL) UA (8 mL)	Pevnar 13 ^{®†}	MenACYW* Pentaxim ^{®‡}	Pevnar 13 ^{®†} Pentaxim ^{®‡}	MenACYW* Pentaxim ^{®‡} ENGERIX-B ^{®§}	BL0002 (6 mL)	MenACYW* MMR**	BL0003 (6 mL) UA (8 mL)
Group 4	BL0001 (6 mL) UA (8 mL)	Pevnar 13 ^{®†}	Pentaxim ^{®‡}	Pevnar 13 ^{®†} Pentaxim ^{®‡}	Pentaxim ^{®‡} ENGERIX-B ^{®§}	BL0002 (6 mL)	MMR**	BL0003 (6 mL) UA (8 mL)

V: Visit, UA: Urinalysis

*MenACYW conjugate vaccine

† No immunogenicity endpoints will be measured for this vaccine in the Russian Federation. The PCV13 routine vaccine recommended at 15 months of age in the Russian Federation is considered as out of scope for this study and will not be provided by the Sponsor but procured by the sites as per their standard practices.

‡ The 4th dose of Pentaxim[®], which is administered at 18 months of age, is considered out of the scope of the study, and it will not be provided by the Sponsor but procured by the sites as per their standard practices. Subjects will be instructed to receive it for completion of the Pentavalent series as per the NIC of the Russian Federation recommendation.

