5.1.3 Statistical Methods for Observational Objectives

No hypotheses will be tested. Descriptive statistics will be presented. Safety results will be described for subjects in all study groups. The main parameters for the safety endpoints will be described by 95% CI using the exact binomial method (Clopper-Person method) (1).

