5.2.3.1 Overall Safety Analysis Set for Any Dose

The overall safety analysis set (SafAS) is defined as those subjects who have received at least 1 dose of the study vaccines and have any safety data available.

-
- Confidential/Proprietary Information
 - Page 62 of 67

All subjects will have their safety analyzed after any dose according to the vaccine received at the first dose.

Safety data recorded for a vaccine received out of the protocol design will be excluded from the analysis (and listed separately).

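### The any-dose safety rule classes subjects by the first vaccine given, so it cannot separate Russian Groups 3 and 4, which both receive only Prevnar 13 at Visit 1

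*SAP*

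**What the plan says.** SAP 5.2.3 classes each per-dose analysis by what was received at that dose. For any-dose analyses it says that "all subjects will have their safety analyzed according to the vaccine received at the first dose". SAP 5.2.3.1 repeats this for the overall safety set: "All subjects will have their safety analyzed after any dose according to the vaccine received at the first dose". Protocol 12.2.2 and 12.2.2.1 carry the same rule, and none of the four places makes an exception for the Russian Federation. A footnote in Protocol 12.2.2 qualifies the term study vaccine as one "for which safety data are scheduled to be collected".

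The Russian schedule is in SAP Table 3.2 and Protocol Table 5.2. At Visit 1 (2 months) both groups receive Prevnar 13 and nothing else. The arms first differ at Visit 2, as SAP 3.1 confirms: "Group 3: MenACYW conjugate vaccine at 3, 6, and 12 months of age".

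On reporting, SAP 5.1.3 says: "Safety results will be described for subjects in all study groups". Observational objective 2 is the safety profile of MenACYW in Group 3. SAP 4.4.1.3 and 4.4.1.4 plan SAE and AESI summaries over the whole study as well as within 7 and 30 days of vaccination.

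**The concern.** The classification variable takes the same value in both Russian arms, so it cannot tell them apart. It works in Mexico, where Groups 1 and 2 receive different meningococcal vaccines at Visit 1.

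The any-dose class matters most for rare and serious events. Each of SafAS1 to SafAS6 is tied to one vaccination age, so an SAE or AESI table covering the whole study needs the overall set. Under the rule as written, that table would have one Russian line. It could not describe Group 3, nor set Group 3 beside Group 4, its only concurrent control.

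**Working it through.** **1. The plan's own figures.** SAP 5.5 gives the chance of seeing at least one event, 1 − (1 − p)^n, as about 95% for four pairs. All four reproduce:

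- n=525, p=0.57%: 0.9503
- n=350, p=0.85%: 0.9496
- n=200, p=1.5%: 0.9513
- n=150, p=2%: 0.9517

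The n=350 cohort is Groups 1 and 3 together (200 + 150).

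**2. Classes under the written rule.** Group sizes are from Protocol 6.5, Visit 1 vaccines from SAP Tables 3.1 and 3.2.

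| Group | n | What distinguishes the group at Visit 1 | Any-dose class |
|---|---|---|---|
| 1 | 200 | MenACYW (plus routine vaccines) | MenACYW |
| 2 | 100 | Menveo (plus routine vaccines) | Menveo |
| 3 | 150 | Prevnar 13 only | Prevnar 13 only |
| 4 | 75 | Prevnar 13 only | Prevnar 13 only |

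The merged class is 150 + 75 = 225, and 225/525 = 42.9%. The MenACYW class holds 200 subjects and 0 of the 150 Group 3 infants.

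**3. Whether the Russian Visit 1 dose counts.** The documents treat it as a dose of study vaccine for safety:

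- Protocol 5.1.4, Russian Visit 1, gives Prevnar 13 under the instruction "Administer the appropriate study vaccines per Operating Guidelines".
- SAP Tables 3.5 and 3.6 schedule solicited reactions at V01 in both groups, which meets the Protocol 12.2.2 footnote.
- SafAS1 (SAP 5.2.3.2) covers Visit 1 with no country limit.

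**4. Where the arms remain separate.** Group 3 receives MenACYW at Visits 2, 4 and 6. SafAS2, SafAS5 and SafAS6 cover exactly those visits and class subjects by what they received there, so they separate Groups 3 and 4.

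**5. What a merged line hides.** Take 2% of 150 = 3 subjects with an event. The size comes from SAP 5.5; the split between arms is an assumption, shown at both extremes. Intervals are Clopper-Pearson 95%: the lower limit is the 0.025 quantile of Beta(x, n − x + 1), the upper the 0.975 quantile of Beta(x + 1, n − x). With x = 0 the lower limit is 0 and the upper is 1 − 0.025^(1/n).

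| Assumed split | Group 3 | Group 4 | Merged line |
|---|---|---|---|
| All in Group 3 | 3/150 = 2.00% (0.41 to 5.73) | 0/75 = 0% (0 to 4.80) | 3/225 = 1.33% (0.28 to 3.85) |
| All in Group 4 | 0/150 = 0% (0 to 2.43) | 3/75 = 4.00% (0.83 to 11.25) | 3/225 = 1.33% (0.28 to 3.85) |

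Opposite patterns print the same line. This illustrates the loss of information; it does not forecast event rates.

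**The case against.** Four arguments can be made for the plan.

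*Russian Prevnar 13 may not count.* Footnotes in Protocol 5.1.4 (Russian Visit 3) and 6.2.2.3 call it out of scope, with no endpoints measured. On that basis the first counted Russian dose would be at Visit 2, where the arms differ. This does not hold for safety. Protocol Table 5.2 and SAP Table 3.2 exclude only immunogenicity endpoints, reactions are recorded at V01, and SafAS1 includes that visit. It does show that the documents are uneven about this vaccine's status.

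*First dose may mean first meningococcal dose.* The protocol sometimes numbers doses that way. Membership of the safety set could be broad while the class is MenACYW, Menveo or none. That would be a sensible rule, but it is not the one written: the text refers to the vaccine at the first dose, and Group 4 never receives a meningococcal vaccine that could define its class. The fix states this idea explicitly.

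*The intent is plain.* SAP 5.1.3, the objectives and the n=350 cohort all point to reporting by group. This stands as evidence of intent. It does not override an explicit classification rule, and no text explains how that rule separates Group 3 from Group 4. The full analysis sets are expressly analysed as randomised, whereas the safety sets follow vaccines received, so randomised group cannot be assumed as the default.

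*The per-visit sets meet objective 2.* They largely do. Group 3 is described after every MenACYW dose, and the 7-day and 30-day windows can be reported by visit. This limits the problem to the any-dose and whole-study summaries.

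**Conclusion.** The rule is wrong as written for the Russian Federation. It puts 225 of 525 planned subjects in one class and none of the 150 Group 3 infants in a MenACYW class. The effect is confined to any-dose summaries and to SAE and AESI summaries over the whole study. The counts assume planned group sizes and vaccination as scheduled.

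A reader might infer three stronger things that the documents do not support:

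- *That the sponsor means to pool the Russian arms, or will.* SAP 5.1.3 points the other way, and no table layout is given. This is a defect of wording.
- *That Group 3 safety goes undescribed.* SafAS2, SafAS5 and SafAS6 describe it after each MenACYW dose, and no data are lost.
- *That the n=350 detection probability is wrong.* It is correct for 350 infants who receive MenACYW. With only the 200 in the literal MenACYW class, the chance at 0.85% would be 1 − (1 − 0.0085)^200 = 0.819. That describes one table line under the faulty rule, not the cohort in SAP 5.5.

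**What to change.** Replace the any-dose sentence in SAP 5.2.3 and 5.2.3.1 with:

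> For any-dose and whole-study safety analyses, subjects are classified within country by the first meningococcal vaccine actually received at any visit (MenACYW, Menveo, or none = routine vaccines only). Subjects randomised to a meningococcal vaccine who never received one are shown under their randomised group with a footnote.

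The existing rule that data for vaccines received outside the protocol design are excluded and listed stays unchanged. Record the change in SAP 5.7 as superseding Protocol 12.2.2 and 12.2.2.1; that section already corrects the protocol's measles cutoff in the same way. Safety belongs to the first of the two analysis steps in SAP 5.7, so the wording should be settled before that step.

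Classing Russian subjects by what they received at Visit 2 looks simpler but leaves a gap. A Group 3 infant who missed MenACYW at Visit 2 and received it later would be classed as routine only. Looking across all visits avoids this, and also gives a class to a Mexican infant with no meningococcal vaccine at Visit 1.

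The cost is one changed rule, one line in SAP 5.7 and one revised derivation, with no new data. The small downside is an as-randomised fallback, within an otherwise as-received classification, for the few subjects who stop before their first meningococcal dose.

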4.4.1.3 Serious Adverse Events

An event will be considered as a serious event if “Yes” is checked for “Serious” in the CRF.

SAEs will be analyzed throughout the study using the following periods:

- Within 7 days after vaccination
- Within 30 days after vaccination
- During the study (i.e., all SAEs occurred during the study)

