4.4.1.4 Adverse Events of Special Interest

An event will be considered as an AESI if “Yes” is checked for “Is the event an AESI?” in the CRF.

AESIs will be analyzed throughout the study using the following periods:

- Within 7 days after vaccination
- Within 30 days after vaccination

During the study (i.e., all SAEs occurred during the study)

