5.2.3.2 Safety Analysis Set for Vaccination at 2 Months of Age

The safety analysis set 1 for vaccination at around 2 months of age (SafAS1) is defined as those subjects who have received the study vaccine at Visit 1 around 2 months of age and have any safety data available. All subjects will have their safety analyzed after the Visit 1 dose according to the vaccines they actually received at Visit 1.

Safety data recorded for a vaccine received out of the protocol design at Visit 1 will be excluded from the analysis (and listed separately).

5.2.3.3 Safety Analysis Set for Vaccination at 3 Months of Age for Russia Only

The safety analysis set 2 (SafAS2) is defined as those subjects who have received the study vaccine at Visit 2 at around 3 months of age for Group 3 and Group 4 in Russia and have any safety data available. Subjects will have their safety analyzed after this dose according to the vaccines they actually received at Visit 2.

Safety data recorded for a vaccine received out of the protocol design at Visit 2 will be excluded from the analysis (and listed separately).

5.2.3.4 Safety Analysis Set for Vaccination at 4 Months of Age for Mexico only

The safety analysis set 3 (SafAS3) is defined as those subjects who have received the study vaccine at Visit 2 around 4 months of age (Group 1 and Group 2) and have any safety data available. Subjects will have their safety analyzed after this dose according to the vaccines they actually received at that visit.

Safety data recorded for a vaccine received out of the protocol design at that visit will be excluded from the analysis (and listed separately).

5.2.3.5 Safety Analysis Set for Vaccination at 4.5 months of Age for Russia Only

The safety analysis set 4 (SafAS4) is defined as those subjects who have received the study vaccine at Visit 3 for Group 3 and Group 4 in Russia at around 4.5 months of age and have any safety data available. All subjects will have their safety

-
- Confidential/Proprietary Information
 - Page 63 of 67

analyzed after this dose according to the vaccines they actually received at that visit.

Safety data recorded for a vaccine received out of the protocol design at that visit will be excluded from the analysis (and listed separately).

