5.2.3.6 Safety Analysis Set for Vaccination at 6 Months of Age

The safety analysis set 5 (SafAS5) is defined as those subjects who have received the study vaccine at Visit 3 (or Visit 4 for Group 3 and Group 4) at around 6 months of age and have any safety data available. All subjects will have their safety analyzed after this dose according to the vaccines they actually received at that visit.

Safety data recorded for a vaccine received out of the protocol design at that visit will be excluded from the analysis (and listed separately).

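### The safety sets exclude data recorded for an out-of-design vaccine with no exception for SAEs or AESIs, which conflicts with the plan to analyse all SAEs and AESIs during the study

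*SAP*

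**What the plan says.** SAP 5.2.3 sets three rules for safety data.

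- Per-dose grouping: "All subjects will have their safety analyzed after each dose according to the vaccine they actually received at that dose".
- Grouping for any-dose analyses: "all subjects will have their safety analyzed according to the vaccine received at the first dose".
- Exclusion: "Safety data recorded for a vaccine received out of protocol design will be excluded from the analysis (and listed separately").

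The exclusion returns in the overall set, SAP 5.2.3.1 ("Safety data recorded for a vaccine received out of the protocol design will be excluded from the analysis (and listed separately")), in SafAS1, SAP 5.2.3.2 ("Safety data recorded for a vaccine received out of the protocol design at Visit 1 will be excluded from the analysis (and listed separately")), and in matching words for SafAS2 to SafAS6 (for example SAP 5.2.3.6: "Safety data recorded for a vaccine received out of the protocol design at that visit will be excluded from the analysis (and listed separately")). Protocol 12.2.2 to 12.2.2.7 carries the same sentences. SAP 5.2.4 sends all safety analyses through these sets.

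The sections that define the serious-event analyses mention no exclusion. SAP 4.4.1.3 gives the widest SAE period as "During the study (i.e., all SAEs occurred during the study"). SAP 4.4.1.4 says "AESIs will be analyzed throughout the study using the following periods", and those periods again extend to the whole study. The endpoint in SAP 4.3.2.2 runs from Day 0 to the last visit.

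**The concern.** An extra or unscheduled dose of the investigational vaccine is an exposure whose serious consequences a reader of the safety tables would expect to see counted. The exclusion as worded would move such an event to a listing. A listing feeds neither the percentages nor the Clopper-Pearson intervals by which SAP 5.1.3 describes safety.

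The rule also leaves a choice open until data are in hand. The trial is open-label and the phrase that triggers the exclusion has no definition, so whether a given serious event is tabulated could be settled after it is known. Protocol 5.1.2 calls this a pivotal Phase III safety study, so the rule should be fixed beforehand.

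**Working it through.** **1. Which doses can be out of design on any reading.** Protocol Tables 5.1 and 5.2 schedule MenACYW in Mexico at Visits 1, 3 and 5 (Group 1) and in the Russian Federation at Visits 2, 4 and 6 (Group 3). No arm is scheduled for it at the Mexican 4-month visit (Visit 2) or at Russian Visits 1 and 3. A MenACYW dose at one of those visits fits no arm's schedule, so even a narrow reading of the exclusion catches it. The slip is conceivable: at the Mexican 4-month visit Group 2 is due a meningococcal vaccine and Group 1 is not.

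**2. What happens to an SAE after that dose.**

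| Rule | Result for the SAE |
|---|---|
| SAP 4.4.1.3, whole-study period | Counted |
| SAP 5.2.3.1, overall set | Excluded and listed |
| SAP 5.2.4, populations | All safety analyses use the safety sets |

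Both results cannot hold for one event, and no section says which prevails. The SAP does not name the set behind the whole-study SAE table; I take it to be the overall SafAS.

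**3. Numerator and denominator.** The rule removes data, not the child. Entry to the overall set needs one dose of study vaccine and any safety data. A child with other, scheduled doses therefore stays in the denominator while the event leaves the numerator, and the rate can only move down.

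**4. Attribution.** Group 1 receives three or four vaccines together at each vaccination visit (Protocol Table 5.1). A systemic SAE cannot be cleanly assigned to one of them, so data recorded for one vaccine is not a programmable condition for such events.

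**5. The plan's own precision figures.** SAP 5.5 gives about 95% probability of seeing at least one event. With P = 1 − (1 − p)^n:

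| n | p | P |
|---|---|---|
| 525 | 0.57% | 0.9503 |
| 350 | 0.85% | 0.9496 |
| 200 | 1.5% | 0.9513 |
| 150 | 2% | 0.9517 |

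These reproduce.

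**6. Effect on detection, by assumption.** The documents give no number of out-of-design doses. Suppose all safety data of a fraction f of children were lost, which is harsher than the rule. Replacing n by n(1 − f), rounded:

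| n | f = 1% | 2% | 5% | 10% |
|---|---|---|---|---|
| 525 | 0.9488 | 0.9470 | 0.9423 | 0.9327 |
| 350 | 0.9478 | 0.9465 | 0.9412 | 0.9320 |
| 150 | 0.9497 | 0.9487 | 0.9432 | 0.9346 |

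The loss is under two percentage points throughout.

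**7. Effect on one rate, as illustration only.** At 0.85% of 350 MenACYW recipients, 350 × 0.0085 = 2.98 events are expected, about 3. If one were excluded and the child kept:

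- 3/350 = 0.86% (95% CI 0.18% to 2.48%)
- 2/350 = 0.57% (95% CI 0.07% to 2.05%)

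The expected number excluded is far smaller. If events fall evenly over exposures and 1% of exposures are out of design, it is 2.98 × 0.01 = 0.03; at 5% it is 2.98 × 0.05 = 0.15.

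**The case against.** A reader might infer that the exclusion flatly contradicts the as-treated sentence beside it, for instance when a Group 4 child is given MenACYW at 3 months. The documents do not establish that. The two sentences can work together: as-treated grouping for a child who receives another arm's scheduled vaccine, and exclusion for a product or dose that belongs to no arm at that visit. MenACYW at 3, 6 or 12 months in the Russian Federation is part of the design, in Group 3. For wrong-arm receipt the per-protocol criteria (SAP 5.2.1.1 and 5.2.1.2) use different words, and preparation or administration errors appear only there. A footnote to Protocol 12.2.2 also ties study vaccine to those with scheduled safety collection. This is an ambiguity.

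A reader might also infer that serious events certainly vanish. They do not. Excluded data are listed separately. Protocol 10.1 requires every SAE to reach the sponsor within 24 hours, Protocol 11.2 reconciles the pharmacovigilance and clinical databases, and the sponsor's safety team reviews data periodically. The whole-study wording of SAP 4.4.1.3 may even be meant to prevail. All of this stands, and it means that oversight of participants is not impaired. It does not settle whether the event enters the reported percentage, because expedited reporting and listings are not the planned analysis.

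Finally, 0.85% is a detectable incidence, not a forecast of SAEs after unplanned doses, so the step from 3/350 to 2/350 is no estimate of what will happen. That stands in full.

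**Conclusion.** The point holds as a conflict between the exclusion in the safety sets and the whole-study SAE and AESI analyses. It does not need a wrong-arm dose: an unscheduled MenACYW dose is caught on the narrowest reading. For wrong-arm scheduled doses, a clash with the as-treated rule is possible but unproven, because the key phrase is undefined.

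The direction is one-sided, towards lower reported rates. The size is unknown and probably small: at assumed out-of-design fractions of 1% to 10%, detection probabilities change little, and the expected count of affected events at the plan's own detectable incidence is well below one at 1% or 5%. The reason to act is that any single serious event after an unplanned exposure should be counted by a rule set in advance. The verdict rests on reading the exclusion literally and on the overall SafAS being the basis of the whole-study tables.

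**What to change.** In SAP 5.2.3 to 5.2.3.7, and in Protocol 12.2.2 to 12.2.2.7 if it is amended:

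1. Define out of protocol design as a dose that belongs to no arm's schedule at that visit in that country. A scheduled dose from the wrong arm then follows the as-treated rule.
2. Limit the exclusion to the tables of solicited reactions and non-serious unsolicited AEs, and keep the separate listing.
3. Keep SAEs, AESIs, deaths and AEs leading to discontinuation in the overall whole-study tables. Group them by the first dose received, as SAP 5.2.3.1 already requires for any-dose analyses, with a footnote naming the out-of-design vaccine. Moving such events to the vaccine actually received would break that grouping and separate numerators from denominators.
4. Add a cross-reference in SAP 4.4.1.3 and 4.4.1.4.

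The definition needs one agreed schedule. Protocol 6.1.1.3 names Group 2 among MenACYW recipients, while Protocol 6.1.2.3 and Table 5.1 assign it Menveo; these passages must be reconciled.

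The cost is a few sentences and some footnotes. The downside is that any serious events after unplanned exposures enter the tables and need explanation. The change should precede the first database lock, because SAP 5.7 makes the data in the first analysis final.
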